### 3.3. Study Definitions and Derived Variables

Unless otherwise specified, the baseline value will be defined as the last value obtained prior to the first vaccination. Vital signs assessed on Day 1 prior to study vaccination will be considered as baseline. Any medical condition that is present at the time that the participant is screened will be considered as baseline and will only be reported as an AE if symptoms related to the condition occur with greater frequency and/or severity after vaccination during the AE reporting period.

Change from baseline is defined as the additive change from baseline, i.e.,  $CHG_{ij} = y_{ij} - y_{i0}$  where  $y_{ij}$  is the measurement for participant  $i$  at time point  $j$  and  $y_{i0}$  is the measurement for participant  $i$  at baseline (prior to vaccination 1).

Fold-rise (FR) from baseline is defined as the multiplicative change from baseline, i.e.,  $FR_{ij} = \frac{y_{ij}}{y_{i0}}$  where  $y_{ij}$  is the response for participant  $i$  at time point  $j$  and  $y_{i0}$  is the response for participant  $i$  at baseline (pre-vaccination 1). Individual FR values will be reported to 1 decimal place.

The peak titer and peak fold-rise are defined as the maximum value for a participant at any time after the first vaccination.

A responder is defined as having  $\geq 4$ -fold increase relative to baseline, i.e.,  $FR_{ij} \geq 4$  for participant  $i$  at post-baseline time point  $j$ . For serum assays, participants are classified as responders or not at Days 8, 29, 36, 57, 64, 85, and 113; for the ALS assay, participants are classified as responders or not at Days 8, 36, and 64.

## 4. INVESTIGATIONAL PLAN

### 4.1. Overall Study Design and Plan

This is a randomized, double-blind, dose-escalating, outpatient, first-in-human study to test the safety and immunogenicity of the CJCV2 vaccine with and without adjuvant ALFQ. A total of approximately 60 generally healthy adult participants (males and non-pregnant, non-lactating females) aged 18-50 years inclusive will be enrolled in 3 cohorts with 20 participants per cohort (Table 1). Each participant will receive three intramuscular (IM) vaccinations spaced 28 days apart. All participants within a cohort will receive the same fixed dose of CJCV2 (1  $\mu$ g, 3  $\mu$ g, or 10  $\mu$ g) and will be randomized to receive the vaccinations with or without the adjuvant ALFQ (200  $\mu$ g 3D-PHAD® and 100  $\mu$ g QS-21 in Sorensen's Phosphate Buffered Saline) with a 1:1 allocation ratio. The first cohort will receive the lowest dose of CJCV2 (1  $\mu$ g) with or without ALFQ, the second cohort will receive the next highest dose of CJCV2 (3  $\mu$ g), and the third cohort will receive the highest dose of CJCV2 (10  $\mu$ g).

As this is a first-in human study, there will be six sentinel participants in each of the 3 cohorts. No more than two sentinels will be dosed per day with a minimum of two hours between dosing. The Safety Review Committee (SRC) composed of the PI, DMID Medical Monitor, and DMID Medical Officer will review safety data from the six sentinel participants through 7 days post first vaccination to determine if the rest of the cohort may be vaccinated. If no safety signal is detected, the remaining 14 participants in the cohort will be vaccinated. The SRC will also review safety data through Study Day 64 from all participants in Cohort 1 prior to starting enrollment of Cohort 2 at the next highest dose. Similar reviews conducted by the SRC will occur after the Cohort 2 sentinels receive their first vaccination prior to enrolling the remainder of Cohort 2, after all Cohort 2 participants have received all vaccinations prior to enrolling the Cohort 3 sentinels, and after the Cohort 3 sentinels receive their first vaccination prior to enrolling the remainder of Cohort 3.

Additional safety oversight will be conducted by an independent Safety Monitoring Committee (SMC) composed of at least 3 voting members with appropriate Phase 1 study expertise to evaluate the safety data from this trial. The SMC will meet prior to study initiation, if a halting rule is met, or if any other safety concerns are identified during the trial (including but not limited to any concerns noted by the SRC during the sentinel or dose escalation safety reviews).

A schedule of study procedures is presented in Table 2.

The vaccinations will be performed by unblinded study staff, but the participant, study staff performing any post-vaccination assessments, and laboratory personnel will be blinded.

This study will utilize direct data entry for data collection, i.e., study staff will enter clinical data directly into electronic Case Report Forms (eCRFs) in real time. Additional details are in the study Manual of Procedures (MOP).

### 4.2. Discussion of Study Design, Including the Choice of Control Groups

Three doses (1  $\mu$ g, 3  $\mu$ g and 10  $\mu$ g) of CJCV2 will be evaluated with and without ALFQ; see Section 4.4.2 for discussion of the selection of these doses.

As this is a first-in-human study, interim safety reviews occurring after 6 sentinel participants in each cohort and before dose escalation in the next cohort are conducted to minimize risks to participants.

This trial does not use a placebo control as the goal is to study safety and reactogenicity of the study vaccine with and without ALFQ.

## 4.3. Selection of Study Population

Cohort 1 was enrolled under protocol v4.0 (25MAY2022), and Cohorts 2 and 3 were enrolled under protocol v6.0 (08MAY2023); the full list of inclusion and exclusion criteria can be found in the specified versions of the protocol. The inclusion and exclusion criteria were updated between the enrollment of Cohort 1 and Cohort 2 to be less restrictive. The major differences are listed below:

- The inclusion criteria in v4.0 required a Body Mass Index (BMI) < 36; this was changed to BMI < 40 in v6.0.
- The exclusion criteria in v4.0 excluded participants with “documented family history of auto-immune conditions”; this was changed to “documented history of auto-immune conditions in a first-degree relative” in v6.0.
- The exclusion criteria in v4.0 excluded participants with “travel to countries with high *Campylobacter* rates (to include Asia, Africa, and Central and South America) within two years prior to dosing.” This exclusion criterion was removed in v6.0.

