6. Participation in a previous *Campylobacter* study or reports having received vaccination against *Campylobacter* within the last 3 years.
7. History of microbiologically confirmed *Campylobacter* infection in the last 3 years.
8. Occupation involving handling of *Campylobacter* bacteria or vaccine products currently or in the past 3 years.
9. Use of immunosuppressive/immunomodulating disease therapy within 90 days
10. Received Ig or other blood products (with exception of Rho D Ig) within 90 days prior to enrollment.
11. Have a history of severe reactions following previous immunization with any licensed or unlicensed vaccine.
12. Known hypersensitivity to any components of vaccine, adjuvant, or diluent.
13. Received or plan to receive a licensed live vaccine within 30 days prior to 1st vaccination and to 30 days after the last vaccination.
14. Received or plan to receive a licensed, inactivated, vaccine within 14 days prior to 1st vaccination to 14 days after the last vaccination, or a seasonal influenza and/or COVID-19 vaccine \pm 7 days from study product vaccination.
15. Individuals in whom the ability to observe possible local reactions at the eligible injection sites (deltoid region) is unacceptably obscured due to a physical condition or permanent body art.
16. Within 14 days prior to vaccination has received an oral or parenteral (including intra-articular) corticosteroid of any dose for 5 or more days, or high-dose inhaled corticosteroids.
 - a. High dose defined per age as using inhaled high dose per reference chart (https://www.nhlbi.nih.gov/files/docs/guidelines/asthma_qrg.pdf)
17. Current or history of alcohol or drug abuse within one year prior to enrollment.

18. Have any diagnosis, current or past, of schizophrenia, bipolar disease, or other psychiatric diagnosis that may interfere with subject compliance or safety evaluations.
19. Have been hospitalized for psychiatric illness, history of suicide attempt, or confinement for danger to self or others within one year prior to enrollment.
20. Are pregnant, breastfeeding, or plan to become pregnant or breastfeed at any given time during the study.
21. Have an acute illness as determined by study clinician licensed to make medical diagnoses and listed on the Form FDA 1572 as the site PI or sub-investigator, within 72 hours prior to enrollment.

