#### 6.3.3. Per Protocol Immunogenicity Population

The Per Protocol (PP) Immunogenicity Population includes all participants in the Full Immunogenicity Population with the following exclusions:

- Data from all available visits for participants found to be ineligible at baseline.
- Data from all visits after major protocol deviations, such as:
  - Receipt of an incorrect study vaccination.
  - Second or third vaccination not received.
  - Second or third vaccination received out of window.
  - Receipt of any of the following:

- Licensed, live vaccine within 30 days of any vaccination.
- Licensed, inactivated vaccine within 14 days of any vaccination.
- Investigational products at any time during study period.
- Data from any visit that occurs out of window.

All protocol deviations will undergo a review prior to database lock, blinded to outcome value to determine if the affected visit and any subsequent visits will be excluded from the PP Immunogenicity Population for the affected participant(s).

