## 6.4. Covariates and Subgroups

The protocol does not define any formal subgroup analyses, and the study is not adequately powered to perform subgroup analyses.

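### Entry criteria were loosened after Cohort 1, so the 1 µg versus 3 and 10 µg immunogenicity contrast can be confounded, and no planned sensitivity analysis addresses this

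*SAP*

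**What the plan says.** SAP section 4.3 states that Cohort 1 was enrolled under protocol v4.0 and Cohorts 2 and 3 under v6.0, and that "The inclusion and exclusion criteria were updated between the enrollment of Cohort 1 and Cohort 2 to be less restrictive". It lists three major differences. On BMI: "The inclusion criteria in v4.0 required a Body Mass Index (BMI) < 36; this was changed to BMI < 40 in v6.0". The family-history exclusion for autoimmune conditions was narrowed to first-degree relatives. v4.0 also excluded travel within two years before dosing to regions with high *Campylobacter* rates; of this the SAP says "This exclusion criterion was removed in v6.0".

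The current protocol (section 4.1.2) still excludes earlier *Campylobacter* study participation or vaccination, occupational handling, and "History of microbiologically confirmed *Campylobacter* infection in the last 3 years".

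Cohort fixes the CJCV2 dose at 1, 3 or 10 µg; only ALFQ is randomized, within cohort (SAP 4.1, 4.4.3). A responder has at least a 4-fold rise over his or her own Day 1 titer (SAP 3.3: "Fold-rise (FR) from baseline is defined as the multiplicative change from baseline"). SAP 11.4 correlates cumulative estimated dose with raw titer, pooling all three cohorts within each ALFQ status (Tables 28–29, Figures 22–31).

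On covariates and subgroups, SAP 6.4 says: "The protocol does not define any formal subgroup analyses, and the study is not adequately powered to perform subgroup analyses". SAP section 15, which lists changes in conduct and planned analyses, does not mention the criteria change. The vital-signs tables carry footnotes on protocol version; the immunogenicity tables do not.

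**The concern.** The protocol aims to assess responses over a range of doses (section 9.1) and names follow-on work at an optimal dose (section 3.1.1), so readers will compare 1 µg with 3 and 10 µg. That comparison coincides with the change in who could enroll.

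The travel criterion matters most, because it was written around *Campylobacter* exposure and both main immunogenicity summaries are sensitive to earlier exposure. A raised Day 1 titer makes a 4-fold rise harder to reach, which could hide a dose effect. A primed participant who boosts strongly could exaggerate one. In the Spearman analyses, a higher pre-existing titer carries straight into the maximum, so exposure that is more common at 3 and 10 µg would look like a dose-response.

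**Working it through.** **1. The plan's own figures.** Three cohorts × two arms × 10 = 60 participants. For 0 events in 10, the exact 95% upper limit is 1 − 0.025^(1/10) = 0.3085, which reproduces the stated 31%.

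**2. Criteria against dose (SAP 4.1, 4.3).**

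| | Cohort 1 | Cohort 2 | Cohort 3 |
|---|---|---|---|
| CJCV2 dose | 1 µg | 3 µg | 10 µg |
| Protocol version | v4.0 | v6.0 | v6.0 |
| BMI limit | <36 | <40 | <40 |
| Two-year travel exclusion | yes | no | no |
| Family-history exclusion | wider | first-degree | first-degree |

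The break lies between 1 µg and the other doses. Cohorts 2 and 3 share criteria, and both ALFQ arms of a cohort always do.

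**3. Responder threshold (SAP 3.3, 6.5).** Capsule IgG has LLOQ 200, and results below it are set to 100. A participant below LLOQ on Day 1 responds at 4 × 100 = 400. One with an assumed Day 1 titer of 800 needs 4 × 800 = 3200. A later titer of 1600 is a fold-rise of 1600/100 = 16 in the first and 1600/800 = 2 in the second. With 10 per arm, one changed classification moves the responder rate by 10 percentage points.

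**4. How easily one recent traveler could enter an arm.** If a share f of those now eligible are recent travelers (assumed; the documents give no figure), the chance of at least one among 10 is 1 − (1 − f)^10: 65% at f = 10% and 97% at f = 30%.

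**5. Pooled Spearman analysis (SAP 11.4).** The planned n is 30 per ALFQ status. The Fisher-Z 95% interval excludes zero when |rho| > tanh(1.96/√27) = 0.360. A simulation of 5,000 replicates had no true dose effect and a log10 titer SD of 0.5. Cumulative dose was three times the planned dose with 15% preparation error. No one was exposed in Cohort 1, a share f was exposed in Cohorts 2–3, and exposed titers were higher by 0.3 or 0.6 log10. All of these are assumptions. Each cell gives mean rho, then the chance that the interval lies wholly above zero.

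| f | +0.3 log10 | +0.6 log10 |
|---|---|---|
| 0% | −0.006; 2.1% | (same) |
| 10% | 0.021; 3.4% | 0.039; 3.8% |
| 20% | 0.043; 4.1% | 0.081; 6.7% |
| 30% | 0.067; 5.8% | 0.126; 9.4% |
| 50% | 0.111; 8.2% | 0.204; 19.0% |

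Restricted to Cohorts 2–3 (n = 20, f = 30%, +0.6), mean rho was −0.004 and the chance 2.8%. The restriction removes the distortion. The price is that rho must exceed tanh(1.96/√17) = 0.443 before the interval clears zero.

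**The case against.** The study is exploratory, tests no hypotheses, and never randomized dose, so cross-dose comparisons were always sequential and unprotected. Much of what a reader needs is already planned: BMI by group (Table 13); Day 1 counts below LLOQ, GMT, minimum and maximum by group (Tables 15–24); Day 1 reverse cumulative distributions; every individual titer (Listing 8); and maximum titer as a separate secondary endpoint without a baseline denominator. All of this stands and limits the weight of the point. It does not supply responder rates that are less dependent on baseline, and it does not touch the pooled correlations.

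Three stronger readings are tempting but not supported.

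- A reader might infer that every dose display treats the cohorts as one population. Summary tables have a column for each dose-by-ALFQ group, solicited and unsolicited adverse event tables are split by cohort, and GMT trend figures are paneled by cohort. Only the Spearman set pools cohorts, and its scatterplots mark them.
- A reader might infer that travel exposure entered only at 3 and 10 µg. The v4.0 rule reached back two years, so older travel was admissible in Cohort 1, and no travel rule removes domestic exposure. The criteria permit a difference; no document shows one.
- A reader might infer that the per-protocol exclusion ("Data from all available visits for participants found to be ineligible at baseline") should apply one set of criteria to all cohorts. SAP 6.3.3 names no version, but section 4.3 ties the criteria to each cohort's version. Judging eligibility under the version in force at enrollment is ordinary practice. A common rule would label validly enrolled Cohort 2–3 participants ineligible.

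**Conclusion.** The point holds as a limited one. The 1 µg versus 3/10 µg immunogenicity contrast can be confounded by eligibility, and the plan neither examines this nor lists it as a change. The 3 versus 10 µg contrast and the randomized ALFQ contrast are unaffected.

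The size is unknown, because nothing in the documents gives travel history, exposure rates, or a link from travel or BMI to Day 1 titer. One reclassified participant is worth 10 points in an arm. A reader might go on to infer a shift of 10 to 30 points, but that requires one to three primed participants per arm in Cohorts 2–3, none in Cohort 1, and each otherwise a responder. None of this is documented. For the pooled correlations, the simulated chance of a falsely positive interval is 3–19% against about 2%. That rests on the assumed SD, exposure shares and titer shifts, and on exposure only ever raising titers.

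**What to change.** - **SAP 11.2:** add a descriptive sensitivity version of Tables 15–16 limited to participants with Day 1 capsule IgG below LLOQ. All then share the imputed denominator of 100, so response means reaching 400 in every group. Day 1 below LLOQ is only a proxy for no prior exposure. Present it without testing, given SAP 6.4.
- **SAP 11.4:** add a Spearman sensitivity analysis in Cohorts 2–3 only, or on fold-rise in place of raw titer. The first narrows the planned dose range to 3–10 µg. The second removes baseline level but not a difference in boosting.
- **SAP section 15:** list the criteria change as a limit on 1 µg versus higher-dose contrasts, and footnote the cross-dose immunogenicity tables, as is already done for vital signs.
- **SAP 6.3.3:** state that per-protocol eligibility is judged under the version in force at enrollment.

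I would not add a table restricted by BMI. It cannot restore the travel criterion, and it leaves the family-history change untouched.

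The cost is SAP wording and re-runs of existing shells on data already collected. The downside is smaller n in arms of 10, and n = 20 instead of 30 for the restricted correlation.

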## 4.4. Treatments

### 4.4.1. Treatments Administered

The investigational products are the vaccine CJCV2 and the adjuvant ALFQ. CJCV2 is a purified HS23/36 CPS of *Campylobacter jejuni* conjugated to CRM197. ALFQ consists of two active components, a synthetic monophosphoryl lipid A, 3D-PHAD®, and QS-21, a purified saponin extracted from the bark of the *Quillaja saponaria* tree.

### 4.4.2. Identity of Investigational Product(s)

#### CJCV2

The vaccine to be evaluated in the current project is a *C. jejuni* capsule conjugate vaccine named CJCV2 produced from an engineered mutant of 81-176 that is lacking an enzyme responsible for the production of a lipooligosaccharide that could potentially trigger GBS. In contrast to the strain used for CJCV1 (which was made from strain 3208), a natural variant of 3208 (named 3208.1) was selected that presents the two *O*-methyl phosphoramidate (MeOPN) transferases in the "on" status to ensure that there is an optimum amount of MeOPN on the capsule. The CPS is conjugated to CRM197, a non-toxic mutant protein of diphtheria toxin at a CPS: CRM197 ratio of 2:1. The CJCV2 vaccine product was manufactured at Inventprise LLC (Redmond, Washington) with final fill and finish completed by The University of Iowa Pharmaceuticals (Iowa City, Iowa), both performed under current Good Manufacturing Practices (cGMP) conditions.

#### ALFQ

ALFQ is composed of ALF55, QS-21, and Sorensen's Phosphate Buffer. ALF55 is a cGMP-manufactured Army Liposome Formulation containing the phospholipids dimyristoyl phosphatidyl choline and dimyristoyl phosphatidyl glycerol, 3D-PHAD® and 55% cholesterol. Cholesterol serves as a structural lipid and binds to QS-21. QS-21 is a purified saponin extracted from the bark of the *Quillaja saponaria* tree. ALFQ was manufactured at the Walter Reed Army Institute for Research Pilot Bioproduction Facility (Silver Spring, Maryland).

## Formulations

The sterile lyophilized CJCV2 product is to be reconstituted in 1 mL of sterile water for injection. The resuspended CJCV2 product will be diluted with sterile 0.9% Sodium Chloride for Injection, United States Pharmacopeia (USP) to a bulk 2x CJCV2 working solution (Cohort 1: 2  $\mu$ g/mL, Cohort 2: 6  $\mu$ g/mL or Cohort 3: 20  $\mu$ g/mL).

For participant-specific formulation, a total of 0.6 mL of the bulk 2x CJCV2 working solution will be transferred and mixed with a vial containing 0.6 mL of the adjuvant ALFQ or 0.6 mL of sterile 0.9% Sodium Chloride for Injection, USP to prepare 1.2 mL of a final 1x CJCV2 formulation (Cohort 1: 1  $\mu$ g/mL, Cohort 2: 3  $\mu$ g/mL or Cohort 3: 10  $\mu$ g/mL). One milliliter will be drawn into a syringe to be injected intramuscularly to achieve the final quantity of deliverable active CJCV2 component as described above and the full dose of ALFQ (200  $\mu$ g 3D-PHAD®, 100  $\mu$ g QS-21) in participants receiving the adjuvant plus CJCV2. Further details of formulation and administration are included in the study MOP.

### 4.4.3. Method of Assigning Participants to Treatment Groups (Randomization)

Enrollment/randomization was performed through the enrollment module in the electronic data capture system maintained by the SDCC (Statistical and Data Coordinating Center).

Eligible participants were randomized and assigned in a 1:1 ratio to CJCV2:CJCV2+ALFQ. The randomization used a block randomization scheme with random block sizes and was stratified by cohort.

### 4.4.4. Selection of Doses in the Study

The doses of CJCV2 were selected because 1  $\mu$ g is thought to be the lowest dose that will stimulate an immune response, 3  $\mu$ g is likely to stimulate an effective immune response, and 10  $\mu$ g is the highest dose that would be practical to use in a multivalent vaccine (the long-term plan for a vaccine against *Campylobacter*). The three-dose regimen and use of ALFQ was based on previous evaluation of a 1st generation *Campylobacter* vaccine named CJCV1 which demonstrated that 2 doses of vaccine using aluminum hydroxide as an adjuvant was safe, but immunogenicity was poor.

### 4.4.5. Selection and Timing of Dose for Each Participant

All participants will receive three doses of vaccine on Days 1, 29, and 57. A fixed dose of CJCV2 will be used for each cohort: 1  $\mu$ g in Cohort 1, 3  $\mu$ g in Cohort 2, and 10  $\mu$ g in Cohort 3. Any participant assigned to receive ALFQ will receive the same fixed dose (200  $\mu$ g 3D-PHAD and 100  $\mu$ g QS-21). Participants in each cohort will be randomized using a 1:1 allocation ratio to receive either CJCV2 alone or CJCV2+ALFQ.

Sentinels will be dosed at least two hours apart with no more than two sentinels per day vaccinated.

Between the time of vaccination of the first six sentinels to 7 days after enrollment of the last sentinels, no new participants will be vaccinated, but screening may continue.

### 4.4.6. Blinding

This is a double-blind study. The CJCV2 vaccine with or without ALFQ will be prepared by the unblinded site pharmacist and will be administered by an unblinded vaccinator. Vaccination will be the only activity performed by the unblinded vaccinator. The unblinded vaccinator will transport the prepared vaccination in a dark colored UV split top bag to maintain the blind. Participants, investigators, study personnel performing any study-related assessments following study vaccine administration, and laboratory personnel performing antibody assays will be blinded to whether the participant received CJCV2 alone or CJCV2+ALFQ.

The randomization scheme will be generated by the SDCC and provided to unblinded study personnel performing study vaccination preparations.

The SMC may receive data in aggregate and presented by treatment group, but without the treatment group identified. The SMC may be unblinded to individual study treatment assignments of participants, as needed to adequately assess safety issues. The SRC may be unblinded to individual study treatment assignments of sentinel participants only, as needed to adequately assess safety before proceeding to enroll non-sentinel participants.

